5.6.1.2.6. Record height and weight

Record the subject's height and weight in the subject's eCRF.

5.6.1.3. Procedures during the study

Note that some of the procedures to be performed during the study (such as recording medical history, checking inclusion/exclusion criteria and history directed physical examination) will also be performed at screening and are described in Section 5.6.1.2.

5.6.1.3.1. Check contraindications, warnings and precautions to vaccination

Contraindications, warnings and precautions to vaccination must be checked at the beginning of each vaccination visit. Refer to Sections 6.5 and 6.6 for more details.

5.6.1.3.2. Assess pre-vaccination body temperature

The axillary, rectal, oral or tympanic body temperature of all subjects needs to be measured prior to any study vaccine administration. The preferred route for recording temperature in this study will be oral/axillary. If the subject has fever [fever is defined as temperature $\geq 37.5^{\circ}\text{C}/99.5^{\circ}\text{F}$ for oral route on the day of vaccination], the vaccination visit will be rescheduled within the allowed interval for this visit (see Table 6).

5.6.1.3.3. Study group and treatment number allocation

Study group and treatment number allocation will be performed as described in Section 5.2.2. The number of each administered treatment must be recorded in the eCRF at Visit 1. The treatment number allocation for the subsequent (cross-over) dose will be performed at Visit 3. The number of the administered treatment (cross-over dose) must be recorded in the eCRF at Visit 3.

5.6.1.3.4. Sampling

Refer to the Module on Biospecimen Management in the SPM for detailed instructions for the collection, handling and processing of the samples.

Blood sampling for immune response assessments

Blood samples will be taken during certain study visits as specified in Section 5.5 List of Study Procedures.

- A volume of approximately 5 mL of whole blood (to provide approximately 1.7 mL of serum) should be drawn from all subjects for each analysis of humoral immune response at Visit 1 and Visit 2. In case a woman gives birth to an infant before Visit 2, a blood sample must be collected from the subject before the cross-over vaccination is given to the subject.
- A volume of approximately 2.5mL of whole blood (to provide approximately 0.75 mL of serum) from the umbilical cord will be collected from all subjects at Visit 3.

After centrifugation, serum samples should be kept at –20°C/ –4°F or below until shipment. Refer to the SPM for more details on sample storage conditions.

5.6.1.3.5. Study Vaccine administration (Amended: 15 July 2015)

- After completing all prerequisite procedures prior to vaccination, one dose of study vaccine will be administered intramuscularly (IM) in the deltoid of the non-dominant arm (refer to Section 6.3 for detailed description of the vaccine administration procedure). If the investigator or delegate determines that the subject's health on the day of administration temporarily precludes vaccine administration, the visit will be rescheduled within the allowed interval for this visit (refer to Table 6).
- The subjects will be observed closely for at least 30 minutes following the administration of the vaccine, with appropriate medical treatment readily available in case of anaphylaxis.
- *The investigators will discuss with the subjects regarding the benefits of cocooning i.e. up to date vaccination of the baby's siblings with DTP-containing vaccines and vaccinating all the household contacts (people living under the same roof) eligible to receive DTP-containing vaccines as per Summary of Product Characteristics (SmPC) of Boostrix and local governmental recommendations in Spain in order to reduce the potential risk of pertussis in neonates. The subjects will be requested to provide the number of household contacts. Additionally the subjects will also be requested for the number of household contacts who refused the visit to site and the reason for refusal for subsequent eligibility determination and vaccination will be documented.*

5.6.1.3.6. Check and record concomitant medication/vaccination and intercurrent medical conditions

Concomitant medication/vaccination must be checked and recorded in the eCRF as described in Section 6.7.

Intercurrent medical conditions must be checked and recorded in the eCRF as described in Section 6.8.

5.6.1.3.7. Physical examination of the newborn

At Visit 3 or after the birth of the child, physical examination of the newborn will be done. The body weight, length, head circumference and Apgar Score will be recorded in the eCRF.

5.6.1.3.8. Breastfeeding status

At Visit 4, the breastfeeding status (i.e. breast milk or formula milk) will be recorded in the eCRF.

5.6.1.3.9. Recording of AEs, SAEs, pregnancies, pregnancy-related AEs and neonate-related AEs

- Refer to Section 8.2 for procedures for the investigator to record AEs, SAEs, pregnancies and pregnancy-related AEs and neonate-related AEs. Refer to Section 8.3 for guidelines and how to report SAE reports and pregnancies to GSK Biologicals.
- The subjects will be instructed to contact the investigator immediately should they manifest any signs or symptoms they perceive as serious.
- At each vaccination visit, diary cards will be provided to the subject. The subject will record body (oral/axillary) temperature and any solicited local/general AEs (i.e. on the day of vaccination and during the next 7 days) or any unsolicited AEs (i.e. on the day of vaccination and during the next 30 days occurring after vaccination). The subject will be instructed to return the completed diary card to the investigator at the next study visit.
- All pregnancy-related AEs and neonate-related AEs will be captured in the diary card from the first receipt of study vaccine/placebo and will end at Visit 4.
- All adverse pregnancy outcomes, listed pregnancy-related and neonate-related AEs of interest will be reported as SAEs. Refer to Section 8.2.2 for details regarding listed pregnancy-related and neonate-related AEs of interest.
- Collect and verify completed diary cards during discussion with the subject on Visits 2, 3 and 4.
- After vaccination, if the subjects observe any large injection site reaction (defined as swelling with a diameter > 100 mm, noticeable diffuse swelling or noticeable increase of arm circumference) during the 8-day follow-up (Day 0-Day 7) period, they will be asked to contact study personnel and to visit the investigator's office for evaluation as soon as possible. The investigator will record detailed information describing the AE on a specific large injection site reaction in the eCRF.
- Any unreturned diary cards will be sought from the subject through telephone call(s) or any other convenient procedure. The investigator will transcribe the collected information into the eCRF in English.

5.6.1.3.10. Study conclusion

The investigator will:

- review data collected to ensure accuracy and completeness
- complete the Study Conclusion screen in the eCRF.

5.6.2. Study procedures for household contacts in Spain**5.6.2.1. Informed Consent**

The signed/witnessed/thumb printed informed consent of the household contact/parent(s)/LAR(s) must be obtained before study participation. If the household contact is below 18 years of age, the parent(s)/LAR(s) should sign the informed consent form, if required by the local laws. The subject has to visit the site to complete the informed consent process.

Refer to Section 5.1 for the requirements on how to obtain informed consent.

5.6.2.2. Check inclusion and exclusion criteria

Check all inclusion and exclusion criteria for household contacts as described in Sections 4.2 and 4.3 before enrolment.

5.6.2.3. Collect demographic data

Record demographic data such as age, gender, ethnicity and relationship to the infant in the household contact's eCRF.

5.6.2.4. Medical history

Obtain the household contact's medical history by interview and/or review of the medical records and record any pre-existing conditions or signs and/or symptoms present in a household contact prior to the vaccination in the household contact's eCRF.

5.6.2.5. Urine pregnancy test

Female household contacts of childbearing potential are to have a urine pregnancy test prior to study vaccine administration. The study vaccine may only be administered if the pregnancy test is negative. Note: The urine pregnancy test must be performed even if the household contact is menstruating at the time of the study visit.

5.6.2.6. Assess pre-vaccination body temperature

The axillary, rectal, oral or tympanic body temperature of all household contacts needs to be measured prior to any study vaccine administration. The preferred route for

recording temperature in household contacts will be axillary. If the household contact has fever [fever is defined as temperature $\geq 37.5^{\circ}\text{C}/99.5^{\circ}\text{F}$ for axillary route on the day of vaccination], the vaccination visit will be rescheduled within the allowed interval for this visit.

5.6.2.7. Vaccine administration

After completing all prerequisite procedures prior to vaccination, one dose of Boostrix will be administered intramuscularly (IM) in the deltoid of the non-dominant arm (refer to Section 6.3 for detailed description of the vaccine administration procedure). If the investigator or delegate determines that the household contact's health on the day of administration temporarily precludes vaccine administration, the visit will be rescheduled within the allowed interval for this visit. Although the vaccine can be administered anytime during the study, it is recommended that the household contact is vaccinated preferably 2 weeks before birth of the infant. The reason for refusal of vaccination by eligible household contacts will be recorded, if applicable.

The household contacts will be observed closely for at least 30 minutes following the administration of the vaccine, with appropriate medical treatment readily available in case of anaphylaxis.

5.6.2.8. Recording of SAEs and pregnancies

Refer to Section 8.2 for procedures for the investigator to record SAEs and pregnancies. Refer to Section 8.3 for guidelines and how to report SAE and pregnancy reports to GSK Biologicals.

5.7. Biological sample handling and analysis

Please refer to the SPM for details on biospecimen management (handling, storage and shipment).

Samples will not be labelled with information that directly identifies the subject but will be coded with the identification number for the subject (subject number).

- Collected samples will be used for protocol mandated research and purposes related to the improvement, development and quality assurance of the laboratory tests described in this protocol. This may include the management of the quality of these tests, the maintenance or improvement of these tests, the development of new test methods, as well as making sure that new tests are comparable to previous methods and work reliably.
- It is also possible that future findings may make it desirable to use the samples acquired in this study for future research, not described in this protocol. Therefore, all subjects in countries where this is allowed, will be asked to give a specific consent to allow GSK or a contracted partner to use the samples for future research. Future research will be subject to the laws and regulations in the respective countries

and will only be performed once an independent Ethics Committee or Review Board has approved this research.

Information on further investigations and their rationale can be obtained from GSK Biologicals.

Any sample testing will be done in line with the consent of the individual subject.

Refer also to the [Investigator Agreement](#), where it is noted that the investigator cannot perform any other biological assays except those described in the protocol or its amendment(s).

If additional testing is performed, the marker priority ranking given in Section 5.7.4 may be changed.

Collected samples will be stored for a maximum of 20 years (counting from when the last subject performed the last study visit), unless local rules, regulations or guidelines require different timeframes or different procedures, which will then be in line with the subject consent. These extra requirements need to be communicated formally to and discussed and agreed with GSK Biologicals.

5.7.1. Use of specified study materials

When materials are provided by GSK Biologicals, it is MANDATORY that all clinical samples (including serum samples) be collected and stored exclusively using those materials in the appropriate manner. The use of other materials could result in the exclusion of the subject from the ATP analysis (See Section 10.4 for the definition of cohorts to be analysed). The investigator must ensure that his/her personnel and the laboratory(ies) under his/her supervision comply with this requirement. However, when GSK Biologicals does not provide material for collecting and storing clinical samples, appropriate materials from the investigator's site must be used. Refer to the Module on Clinical Trial Supplies in the SPM.

5.7.2. Biological samples

The biological samples are presented in [Table 7](#).

Table 7 Biological samples

Sample type	Quantity*	Unit	Time-point
Blood	5	mL	Day 0 (Pre-Vacc) and Day 30 (Post-Vacc)
Cord Blood	2.5	mL	At Birth

* Approximate quantity

5.7.3. Laboratory assays

Please refer to [APPENDIX A](#) for the address of the clinical laboratories used for sample analysis.

At Visits 1, 2 and 3, blood will be collected for measurement of immune response. All serology will be determined in GSK Biologicals' laboratories, or in a laboratory designated by GSK, using standardized, validated procedures with adequate controls (refer to [Table 8](#)).

Table 8 Humoral Immunity (Antibody determination)

System	Component	Method	Kit / Manufacturer	Unit	Cut-off**	Laboratory†
SER	Corynebacterium diphtheriae.Diphtheria Toxoid Ab.IgG	ELI	NA	IU/ml	.1	GSK Biologicals*
SER	Clostridium tetani.Tetanus Toxoid Ab.IgG	ELI	NA	IU/ml	.1	GSK Biologicals*
SER	Bordetella pertussis.Pertussis Toxin Ab.IgG	ELI	NA	EU/ml	5	GSK Biologicals*
SER	Bordetella pertussis.Filamentous Hemagglutinin Ab.IgG	ELI	NA	EU/ml	5	GSK Biologicals*
SER	Bordetella pertussis.Pertactin Ab.IgG	ELI	NA	EU/ml	5	GSK Biologicals*

SER = Serum

ELI = Enzyme-linked immunosorbent assay (ELISA)

NA = Not Applicable

IU/ml = International units/millilitre

EU/ml = ELISA units/millilitre

*GSK Biologicals laboratory refers to the Global Vaccines Clinical Laboratories (GVCL) in Rixensart, Belgium; Wavre, Belgium.

** These cut-offs might be subject to change due to assay re-development.

†Refer to [APPENDIX A](#) for the laboratory addresses.

The GSK Biologicals' clinical laboratories have established a Quality System supported by procedures. The activities of GSK Biologicals' clinical laboratories are audited regularly for quality assessment by an internal (sponsor-dependent) but laboratory-independent Quality Department.

5.7.4. Biological samples evaluation

5.7.4.1. Immunological read-outs

The immunological read-outs are presented in [Table 9](#).

Table 9 Immunological read-outs

Blood sampling time-point		No. subjects	Component	Components priority rank
Type of contact and time-point	Sampling time-point			
Visit 1 (Day 0)	Pre-Vacc	All	PT, PRN and FHA	1
			D, T	2
Visit 2 (Day 30)	Post-Vacc	All	PT, PRN and FHA	1
			D, T	2
Visit 3 (At birth)	At birth	All*	PT, PRN and FHA	1

Pre-vacc: Blood sample to be collected before the dose of the booster vaccination in pregnant women (Visit 1).

Post-vacc: Blood sample to be collected one month after the booster vaccination in pregnant women (Visit 2).

* Cord blood collected from umbilical cord of subjects

In case of insufficient blood sample volume to perform assays for all antibodies, the samples will be analysed according to priority ranking provided in [Table 9](#).

5.7.5. Immunological correlates of protection

The following cut-offs are accepted as immunological correlates of protection:

- Specific antibodies against diphtheria toxoid (anti-diphtheria) and tetanus toxoid (anti-tetanus) will be measured by Enzyme-linked immunosorbent assay (ELISA). The assay cut-off of ELISA is currently set at 0.1 International Units per ml (IU/ml), which provides a conservative estimate of the percentage of subjects deemed to be protected [[Camargo, 1984](#); [Melville-Smith, 1983](#)].
- No serological correlate of protection against pertussis has been established [[Plotkin, 2010](#)]. Antibodies against the pertussis components pertussis toxoid (PT), filamentous haemagglutinin (FHA) and pertactin (PRN) will be measured by ELISA. The seropositivity cut-off for all three pertussis antibodies in ELISA is currently 5 EL.U/ml. Subjects with antibody concentration below the cut-off will be considered seronegative.

The immunological assay results will be communicated to the investigator as soon as they become available and in any case no later than 12 months after the visit date at which sampling allows the assessment of immunogenicity.

The investigator is encouraged to share the immunological assay results for non-responders with the study subjects.

For the study subjects identified as non-responders, it remains the responsibility of the study investigator in charge of the subject's clinical management to determine the medical need for re-vaccination and to re-vaccinate the subjects as per local/regional practices.

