Adequate contraception does not apply to subjects of child bearing potential with same sex partners, when this is their preferred and usual lifestyle.

Adverse event: Any untoward medical occurrence in a patient or clinical investigation subject, temporally associated with the use of a medicinal product, whether or not considered related to the medicinal product.

An adverse event (AE) can therefore be any unfavourable and unintended sign (including an abnormal laboratory finding), symptom, or disease (new or exacerbated) temporally associated with the use of a medicinal product. For marketed medicinal products, this also includes failure to produce expected benefits (i.e. lack of efficacy), abuse or misuse.

Blinding: A procedure in which one or more parties to the trial are kept unaware of the treatment assignment in order to reduce the risk of biased study outcomes. The level of

blinding is maintained throughout the conduct of the trial, and only when the data are cleaned to an acceptable level of quality will appropriate personnel be unblinded or when required in case of a serious adverse event. In an observer-blind study, the subject and the site and sponsor personnel involved in the clinical evaluation of the subjects are blinded while other study personnel may be aware of the treatment assignment (see Section 5.3 for details on observer-blinded studies).

- Child in care:** A child who has been placed under the control or protection of an agency, organisation, institution or entity by the courts, the government or a government body, acting in accordance with powers conferred on them by law or regulation. The definition of a child in care can include a child cared for by foster parents or living in a care home or institution, provided that the arrangement falls within the definition above. The definition of a child in care does not include a child who is adopted or has an appointed legal guardian.
- Congenital anomalies:** The collection of congenital anomalies is based on the Centers for Disease Control and Prevention (CDC) Metropolitan Atlanta Congenital Defects Program (MACDP) guidelines [CDC, 2007] and include morphological, functional, chromosomal or genetic anomalies, regardless of whether detected at birth or not, the foetus is delivered dead or alive, or defects are identified by prenatal ultrasound, amniocentesis or examination of the products of conception.

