5.3. Method of blinding

Data will be collected in an observer-blind manner. By observer-blind, it is meant that during the course of the study, the vaccine recipient and those responsible for the evaluation of any study endpoint (e.g. safety, reactogenicity) will all be unaware of which vaccine was administered. To do so, vaccine preparation and administration will be done by authorised medical personnel who will not participate in any of the study clinical evaluation assays.

The laboratory in charge of the laboratory testing will be blinded to the treatment, and codes will be used to link the subject and study (without any link to the treatment attributed to the subject) to each sample.

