5.4.1. Independent Data Monitoring Committee

An IDMC will monitor the safety aspects of *Boostrix* in the clinical study. An IDMC including an obstetrician, paediatrician, statistician and a neonatologist will be in charge of monitoring the safety aspects of the study and the committee will meet at regular intervals to review data on other adverse pregnancy outcomes. The frequency of the meeting will be decided in consultation with the chairman of the committee.

To facilitate the review, the IDMC will be provided with all relevant safety data including data on congenital anomaly/foetal malformation/ incidence of grade 3 local and general solicited adverse events, withdrawals due to adverse experiences and SAE data at specified times and access to data on request by an unblinded statistician. The GSK staff and other study staff will be blinded during this study.

The IDMC will have access to the individual codes and may at its discretion, decode the cases to identify the product administered to any subject and evaluate whether enrolment in the study should be halted or if any additional safety follow-ups are required for subject safety.

The operating rules of the IDMC will be established by GSK and will be documented by a charter.

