8.2.4.2.2. Assessment of causality

The investigator is obligated to assess the relationship between investigational vaccine and the occurrence of each AE/SAE. The investigator will use clinical judgement to determine the relationship. Alternative plausible causes, such as natural history of the underlying diseases, concomitant therapy, other risk factors, and the temporal relationship of the event to the investigational vaccine will be considered and investigated. The investigator will also consult the IB to determine his/her assessment.

There may be situations when a SAE has occurred and the investigator has minimal information to include in the initial report to GSK Biologicals. However, it is very important that the investigator always makes an assessment of causality for every event prior to submission of the Expedited Adverse Events Report to GSK Biologicals. The investigator may change his/her opinion of causality in light of follow-up information and update the SAE information accordingly. The causality assessment is one of the criteria used when determining regulatory reporting requirements.

In case of concomitant administration of multiple vaccines, it may not be possible to determine the causal relationship of general AEs to the individual vaccine administered. The investigator should, therefore, assess whether the AE could be causally related to vaccination rather than to the individual vaccines.

All solicited local (injection site) reactions will be considered causally related to vaccination. Causality of all other AEs should be assessed by the investigator using the following question:

Is there a reasonable possibility that the AE may have been caused by the investigational vaccine?

- YES : There is a reasonable possibility that the vaccine contributed to the AE.
- NO : There is no reasonable possibility that the AE is causally related to the administration of the study vaccine(s). There are other, more likely causes and administration of the study vaccine is not suspected to have contributed to the AE.

If an event meets the criteria to be determined as ‘serious’ (see Section 8.1.2), additional examinations/tests will be performed by the investigator in order to determine ALL possible contributing factors for each SAE.

Possible contributing factors include:

- Medical history.
- Other medication.
- Protocol required procedure.
- Other procedure not required by the protocol.
- Lack of efficacy of the vaccine, if applicable.

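### Protocol 5.7.5 has no hold on subject-level antibody results, so they could reach blinded investigators and women before Visit 4 and partly reveal allocation

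*Protocol*

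**What the plan says.** On release, Protocol 5.7.5 states: "The immunological assay results will be communicated to the investigator as soon as they become available". The only time limit is a latest one: "in any case no later than 12 months after the visit date at which sampling allows the assessment of immunogenicity". The same section adds: "The investigator is encouraged to share the immunological assay results for non-responders with the study subjects". It then leaves the follow-up of each non-responder to the investigator. Those last two provisions only make sense if the results are identifiable by subject.

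On blinding, Protocol 5.3 requires that "the vaccine recipient and those responsible for the evaluation of any study endpoint (e.g. safety, reactogenicity) will all be unaware of which vaccine was administered". The Blinding entry in the protocol glossary says that the level of "blinding is maintained throughout the conduct of the trial, and only when the data are cleaned to an acceptable level of quality" are appropriate personnel unblinded, with an exception for serious adverse events. Protocol 5.4.1, on the data monitoring committee, says: "The GSK staff and other study staff will be blinded during this study".

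Section 5.3 also blinds the laboratory to treatment, but it does not limit what the laboratory or sponsor may send to sites. The SAP does not mention release of results.

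**The concern.** The person who receives the serology is the person who makes the safety judgements. Protocol 8.2.4.2.2 treats solicited local reactions as related by rule and then says: "Causality of all other AEs should be assessed by the investigator using the following question". Protocol 8.2.4.2.1 has the investigator grade unsolicited events. SAEs and the listed pregnancy and neonatal events are collected to Visit 4 (8.2.1), and the investigator may revise an SAE causality opinion later (8.2.4.2.2). The women, who are also meant to be blinded, fill in the diary cards.

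The comparator contains no antigen (Table 10, sodium chloride). Vaccine response to the pertussis antigens needs a two-fold or four-fold rise, or four times the cut-off in seronegative women (10.5). Section 5.7.5 does not define a non-responder. If the 10.5 definition is meant, most women so labelled would be expected to be controls, although the documents give no rate.

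At stake are the tabulations of related and Grade 3 events (10.8). Existing safeguards would not detect the problem. Emergency unblinding is documented (8.7), and subjects whose code is broken leave the ATP cohorts (10.4.2; SAP elimination code 1060). Inferring the arm from a titre triggers neither.

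**Working it through.** **1. What could be released, and when.** Table 9 tests five antibodies in each woman at Visits 1 and 2, and three pertussis antibodies in cord blood at Visit 3. No post-dose result can exist before Visit 2.

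**2. Longest possible exposure.** Assumptions: delivery at 40 weeks (280 days) and the optimal intervals in Table 6 (Visit 2 at day 30, Visit 4 at 60 days after Visit 3).
- Dosed at 27 weeks (189 days): delivery is 280 − 189 = 91 days after Visit 1. Visit 2 to Visit 4 is 91 − 30 + 60 = 121 days.
- Dosed at 36 weeks 6 days (258 days): delivery is 22 days after Visit 1, before day 30. The note to Table 4 then combines Visits 2 and 3, so the window is 60 days.
- Cord sample to Visit 4: 45 to 75 days is allowed.

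The upper bound is therefore 60 to 121 days, less the assay turnaround, which is not given. With testing after Visit 4 it is zero. The 12-month limit is longer than the roughly 5 months each woman is in the study, so it neither forces nor prevents early release.

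**3. The plan's own figure.** The inputs for separation are the Table 16 ratios and log10 SDs, so I first checked that they reproduce its power. Anti-PT: difference log10(2.3) − log10(1.5) = 0.1856; standard error 0.577 × √(2/272) = 0.0495; power = Φ(0.1856/0.0495 − 1.96) = 96.3%, against 96% stated. Anti-FHA and anti-PRN exceed 99.9%, so overall power is 96.3%, which agrees with the plan.

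**4. How well one cord-blood result separates the groups.** Assuming normal log10 values with equal SD and equal group sizes, d = log10(ratio)/SD, AUC = Φ(d/√2), and the best single cut classifies Φ(d/2) correctly (50% is chance).
- Anti-FHA or anti-PRN: d = 0.699/0.564 = 1.239; AUC 0.81; 73% correct.
- Anti-PT: d = 0.3617/0.577 = 0.627; AUC 0.67; 62% correct.

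**5. Three antigens together (needs an assumption).** The documents give no between-antigen correlation. Assuming a common correlation from 0 to 0.8, the combined AUC is 0.85 to 0.91, with 77% to 82% correct. At zero correlation, D = √(0.627² + 2 × 1.239²) = 1.861 and AUC = Φ(1.861/√2) = 0.91.

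**6. The maternal rise from Visit 1 to Visit 2.** This needs the group ratio in maternal serum and the SD of the within-woman change. Table 16 powers the primary comparison, which 10.1 places in cord blood, so it supplies neither. I give no figure for the rise.

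**The case against.** The case against is substantial, and much of it stands.

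- **There is no outright contradiction.** A reader might infer that 5.7.5 and 5.3 cannot both be followed. They can: if assays finish after Visit 4 and within 12 months, both are met. The conflict is conditional on timing. This stands.
- **Early release is not shown.** Serum is frozen until shipment (5.6.1.3.4), and SAP section 9 says the assays were re-developed and re-validated during the study, which suggests later testing without proving it. The Study Procedures Manual is not among these documents and might restrict release. This stands as uncertainty. It is not a safeguard, because the blind then depends on laboratory scheduling that the plan does not fix.
- **The results are not an allocation list.** A reader might infer near-complete unblinding from the pre/post pattern. The only computable separation is for cord blood, and a single result misclassifies 27% to 38% of women. This stands; Table 16 calls its inputs conservative, so true separation may be larger, by an unknown amount.
- **The exposed data are limited.** The dose-1 solicited window (Days 0–7) has closed, and the 31-day window nominally so, before a post-dose result can exist. Listed events are reported whatever their intensity or presumed cause (8.2.2), against written definitions, and several, such as preterm birth and death, are objective. This stands. Causality of SAEs and of solicited general symptoms after the post-delivery dose remains a judgement.
- **Secondary objectives are descriptive** (10.9; SAP section 7). This is true, but descriptive safety tables can still be biased.

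**Conclusion.** The concern holds in conditional form. As written, 5.7.5 permits subject-level serology to reach investigators, and through them the women, while both are required to be blinded and safety is still being recorded. Nothing in either document prevents this.

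Where results arrive before Visit 4, allocation is partly revealed: AUC 0.81 for one cord anti-FHA or anti-PRN result and 0.67 for anti-PT, on the Table 16 assumptions. The risk is confined mainly to investigator causality and intensity judgements on unsolicited events and SAEs after Visit 2, and to diary reporting after the post-delivery dose. A reader might also infer that the primary GMC ratio is compromised. The documents do not support that, since it is measured by a laboratory blinded to treatment. Whether any exposure occurred cannot be determined from the documents.

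**What to change.** State in 5.7.5 that no subject-level immunogenicity result goes to sites or subjects before all Visit 4 data at that site are complete and frozen, or before study unblinding. State also that the laboratory and sponsor send no such result earlier.

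Two other provisions of 5.7.5 must be reconciled with this hold. The 12-month limit could be exceeded for women enrolled early, since the length of enrolment is not given. The text on sharing non-responder results and on their follow-up depends on when results arrive. No clinical rule is proposed here.

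If results have already been issued, the sponsor can compare each release date with that woman's Visit 4 date and report any that came first.

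The cost is a short amendment and later receipt of results by sites. The planned 340 women per group, the 272 evaluable and the power are unchanged.
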